5.2 NETWORK SUBJECT ENROLLMENT

A list of each consenting patient's network members will be obtained during the patient baseline questionnaire completion as described above. The most influential network members will be ranked based on their network position, driving distance from the patient, speaking frequency, and whether they have high blood pressure. Network members able to participate in this study may include anyone identified by the study participant anywhere in the United States. Potential network members for the patient randomized to the intervention arm will be called by the patient along with study staff to introduce them to the study. If the network member is interested in participating, they will be sent a text message or email (per their preference and as detailed above in Section 4.2b) with a link to REDCap containing the study fact sheet for their review and electronic consent in which network members select "I agree" if they would like to participate.

We request a waiver of written documentation of informed consent for network members providing electronic consent. We believe this is justified for several reasons. First, this study presents no more than minimal risk to the network members seeing as their only task will be to join the counseling session and offer support to the patient. Further, the only record linking the subject and the research would be the consent document and the principal risk would be potential harm resulting from a breach of confidentiality. For this reason, the study team believes that a waiver of documentation of informed consent with an electronic Consent Fact Sheet including contact information to study staff and an opportunity to discuss questions/concerns will be the best consent process for network members participating in this study.

Additional network-subjects are allowed to join at any point throughout the 12-week study period, but only at the request of the index patient-subject. These additional members will be required to complete the consent process described above prior to being included in the Group SMS thread or being invited to participate in any of the study sessions.

6. STUDY PROCEDURES

6.1 Consent/Enrollment and Baseline Visit

The study staff will meet with the eligible patients at bedside, explain the study to the patient, and obtain written informed consent using MGB-approved REDCap digital signature consent process. The consent form will include consent for enrolled participants to receive follow-up outreach after

completion of the trial to participate in an implementation evaluation, to include either a brief survey or a brief qualitative interview. Study staff will then help the patient complete baseline questionnaires consisting of the validated PERSNET social networks questionnaire, stroke information, and the CES-D depression screen. Additional covariates, such as medication use, will be retrieved from the EHR. The PERSNET resulting network map will be used to identify network team members. Participants will then be randomized to either the Social Networks (intervention) arm or the Individual Counseling (control) arm. In the Individual Counseling arm, while the patient's network will be mapped, it will not be acted upon. In the Social Network arm, network members identified will be invited to participate in the study per the enrollment description above (Section 5.2). All patients will be provided with a wide-range blood pressure cuff (Medline MDS4001 blood pressure monitor) and instructions for weekly home monitoring. Patient will be asked to use this cuff to collect a baseline blood pressure measurement at the time of enrollment. A blood pressure measurement will also be collected from the patient's EHR on the day of discharge from the hospital. Finally, patients will be offered several Zoom meeting options and will schedule the first counseling session with study staff based on their availability.

Both this study and protocols 2020P003739 and 2020P000320 ask patients to complete the PERSNET social networks questionnaire. To simplify the enrollment process, patients that have consented to participate in both studies will only be asked to complete these questionnaires once for protocol 2022P000444. Data from these questionnaires will then be shared with protocols 2020P003739 and 2020P000320.

6.2 Between Study Visits

Upon enrollment of the patient-subject and their network members in the **Social Networks arm**, study staff will use an MGB-approved and properly configured study-specific cellular device to initiate a group SMS thread containing the index patient-subject, their consented network members (if applicable), and their assigned RA/study staff. This group SMS thread will be utilized for three types of communication: 1) appointment reminders from study staff, 2) facts/tips related to blood pressure control from study staff, and 3) organic correspondence between the patient and network members. Correspondence from study staff will be scripted (see "*Text message list*" attachment). Study staff will also collect email addresses from patients at baseline to use for back-up communication. Patients will be read the following MGB-required warning language regarding unsecure email by study staff: *"The Mass General Brigham standard is to send email securely. This requires you to initially set up and activate an account with a password. You can then use the password to access secure emails sent to you from Mass General Brigham. If you prefer, we can send you "unencrypted" email that is not secure and could result in the unauthorized use or disclosure of your information. If you want to receive communications by unencrypted email despite these risks, Mass General Brigham will not be held responsible. Your preference to receive unencrypted email will apply to emails sent from this research group/study only."* The study staff will then obtain verbal permission to send unencrypted email and document within REDCap prior to sending any unsecure email. If necessary, study staff will follow up with patients over secure or unsecure email (per their preference) using the subject line "Follow-up for TEAMS-BP Study" if they are unable to make contact with the patient by phone after they are discharged from the hospital. All secure email communication will be sent using the SEND SECURE encryption mechanism and communication will resume on the cellular device if possible once contact has been made.

Upon enrollment of patient-subjects in the **Individual Counseling arm**, study staff will use an MGB-approved and properly configured study-specific cellular device to initiate an SMS thread with the

patient-subject. This SMS thread will be utilized for two types of communication: 1) appointment reminders and 2) facts/tips related to blood pressure control from study staff. Correspondence from study staff will be scripted (see “Text message list” attachment). Study staff will also collect email addresses from patients at baseline to use for back-up communication. Patients will be read the following MGB-required warning language regarding unsecure email by study staff: *“The Mass General Brigham standard is to send email securely. This requires you to initially set up and activate an account with a password. You can then use the password to access secure emails sent to you from Mass General Brigham. If you prefer, we can send you “unencrypted” email that is not secure and could result in the unauthorized use or disclosure of your information. If you want to receive communications by unencrypted email despite these risks, Mass General Brigham will not be held responsible. Your preference to receive unencrypted email will apply to emails sent from this research group/study only.”* The study staff will then obtain verbal permission to send unencrypted email and document within REDCap prior to sending any unsecure email. If necessary, study staff will follow up with patients over secure or unsecure email (per their preference) using the subject line “Follow-up for TEAMS-BP Study” if they are unable to make contact with the patient by phone after they are discharged from the hospital. All secure email communication will be sent using the SEND SECURE encryption mechanism and communication will resume on the cellular device if possible once contact has been made.

Upon initiation of the group SMS thread, study staff will send a text message with the date, time and Zoom meeting link for the first session based on the time agreed upon with the patient during the enrollment visit.

Text messages will only be read during regular business hours (Monday through Friday, 9AM – 5PM Eastern Time). Texts sent on nights, weekends or holidays will not be read until the following business day. If any participant sends a text message prompting a response to the study staff, the staff will respond utilizing minimum necessary MGB principles. For the following participant responses, automatic action will be taken with messages as follows:

Patient Response	Automated action or text back to patient
Stop	<Stop text messages>
Quit	<Stop text messages>
Thank you	You're welcome - keep up the good work!
Thanks	You're welcome - keep up the good work!
Ok	<No response>
<Response requiring medical attention>	This phone number is used for study purposes only and is not monitored by a licensed healthcare professional. If you need medical help, please contact your 24-hour nurse helpline, call 911, or go to your nearest ER.
<Other response>	<Minimum necessary response per MGB principles>

6.3 Counseling Sessions

All counseling sessions will take place remotely through Zoom, an MGB-approved secure video platform. In both the individual counseling and social network arm, participants will meet with the study nurse with an RA present on weeks 2,6, and 12 (+/- 7 days).

6.3a Counseling Session 1—On Week 2 (+/- 7 days)

The first counseling session will take place two weeks after initial enrollment. Study staff will ensure that only participants who have completed the consent process join the Zoom meeting.

Individual Counseling Arm

Patients in the individual counseling arm will meet individually with the study nurse. The nurse will provide counseling on the basics of blood pressure, taking and adjusting medications, monitoring blood pressure, reducing salt, and being physically active. The patients will then schedule their next session and collect a blood pressure measurement with cuff provided by the study staff under direct supervision by the nurse.

Social Network Arm

At the beginning of this session, the Research Assistant/study staff will confirm that all network-participants have completed the electronic consent process via REDCap.

The study nurse will begin the team-based counseling session in which she will provide counseling on teamwork and the same blood pressure control topics covered with the individual counseling group. The teamwork specific topics will include how networks can work together as a team, communication tips for engaging with one another and spreading positive messages and establishing the roles and responsibilities of each network team member. The team will schedule the following session and the patient will collect a blood pressure measurement with the cuff provided by the study staff under direct supervision by the nurse.

6.3b Counseling Session 2—On Week 6 (+/- 7 days)

The second counseling session will take place six weeks after initial enrollment. Participants in both arms will have received text messages every week in the three weeks between session 1 and session 2. Study staff will ensure that only participants who have completed the consent process join the Zoom meeting.

Individual Counseling Arm

Patients in the individual counseling arm will again meet individually with the study nurse who will review information about taking and adjusting medications, monitoring blood pressure, reducing salt, and being physically active. The patients will also collect a blood pressure measurement with cuff provided by the study staff under direct supervision by the study nurse.

Social Network Arm

Patients in the social network arm will again meet with their network members and the study nurse to review information about teamwork in the context of taking and adjusting medications, monitoring blood pressure, reducing salt, and being physically active that were covered in session 1. The nurse will work with the team for a revised plan, if necessary, to achieve optimal blood pressure by the final session. The patients will also collect a blood pressure measurement with cuff provided by the study staff under direct supervision by the study nurse.

6.4 End line Study Session—On Week 12 (+/- 7 days)

The third counseling session will take place twelve weeks after initial enrollment. Participants in both arms will have received text messages every week in the five weeks between sessions 2 and 3. Study staff will ensure that only participants who have completed the consent process join the Zoom meeting.

Individual Counseling Arm

Patients in the individual counseling arm will meet for a final time with the study nurse. In this session, the patient will check their blood pressure under direct video observation by the nurse. The nurse will also assess the study's secondary outcomes by taking note of the patient's blood pressure in relation to post-stroke hypertension treatment goal of <130/80 and the patient-reported physical function (based on the NIH PROMIS physical function sub-scale). Participants' social networks will be mapped to assess changes that may have occurred as a result of this study.

Social Network Arm

Patients in the social network arm will meet with their network team and the study nurse for a final time. In this session, the study nurse will first conduct a semi-structured interview with the patient and network members to assess the process and effectiveness of the sessions, as well as their views on their teamwork over the course of the intervention (see "*Interview Guide*" attachment). Prior to the interviews, subjects will be asked to provide verbal consent for audio recording of the interview. Patients will not be forced to participate and may withdraw their consent to participate at any time. Participants will be informed that participation is voluntary and that the interviews are part of the research study. The semi-structured interviews after the will be audio recorded, transcribed by the study team or by Landmark Associates (with whom MGB has a BAA agreement) and analyzed using qualitative software to identify themes using a grounded theory approach.

All network members will then be asked to leave the Zoom meeting, except for the primary caregiver (if applicable). The patient will collect a final blood pressure measurement under direct supervision of the study nurse, complete the PROMIS physical function scale, and remap their network with the PERSNET instrument to assess any changes that may have occurred as a result of the study. The primary caregiver network member will be asked to complete the caregiver burden scale which will be sent to them via a link in the Zoom chat or via text message.

Outcomes

The primary outcome of the study will be absolute reduction in systolic blood pressure at 3 months. Secondary outcomes will be attainment of a post-stroke hypertension treatment goal and patient-reported physical function. Feasibility measures will also be assessed throughout the intervention. End line caregiver burden will be measured in the social network arm compared to historical control data.

The intervention process evaluation conducted using semi-structured qualitative interviewing during the final session (Social Networks arm) will be analyzed using qualitative software to identify themes using a grounded theory approach. Once the data are analyzed, the investigators will review the findings to consolidate observations into a common set of themes.

Finally, a shortened version of the validated PERSNET utilizing only a subset of the initial questionnaire will be tested for predictive accuracy against the results of the full validated PERSNET scale.

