5.1 PATIENT SUBJECT ENROLLMENT

The study staff will perform daily screening of hospital admissions based on the study’s inclusion and exclusion criteria listed above. If an inpatient meets criteria, the study staff will directly approach the nurse, physician attending, or physician assistant who is caring for the patient to briefly explain the study and determine an appropriate time to meet with the patient. We will verify the inclusion and exclusion criteria with the treating provider. If permission is granted by the treating provider, the study staff will meet with the patient at bedside, explain the study to the patient, and ask the remaining exclusion criteria to confirm their eligibility. In particular, the study staff will confirm that the patient has a phone and is capable of sending and receiving text messages. Study staff will also ensure that patients are willing to engage network members in the study if assigned to the intervention arm. If the patient is interested in participating in the study, the study staff will then obtain informed consent from the patient using MGB-approved REDCap digital signature consent process, conduct baseline surveys, randomize the patient and, for intervention arm participants, collect contact information for their network members who will be directly contacted and invited to participate. Patients will be stratified according to network size (<5 vs 5 or more) and location of hospitalization (MGH or BWH), and then be randomized using a 1:1 ratio to receive individual hypertension counseling or the social network intervention.

Patients who are eligible for participation in this study and two other IRB approved studies led by [name] ([name], 2020P003739 and 2020P000320) may be approached for participation in both studies within one enrollment visit. Study staff will explain both studies and emphasize that patients can choose to only participate in one of the studies. If interested, patients will be provided consent forms for both studies and will agree to participate in each study separately. Patients will then go through baseline questionnaires for both studies, completing any repeated questionnaires between both studies only once. Participation in the three studies will otherwise be separate.

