9.3 Statistical analysis

The primary outcome will be absolute reduction in systolic blood pressure at 3 months. Secondary outcomes will be attainment of a post-stroke hypertension treatment goal of <130/80 and patient-reported physical function (based on the NIH PROMIS physical function sub-scale). These outcomes will be evaluated, for intervention and control patients, on a 10-minute Zoom exit interview with direct observation on video by the study nurse.

Analysis will be conducted using intention-to-treat principles. Evaluation of the primary outcome and physical function secondary outcome will be completed using linear controlling for any differences in baseline variables despite randomization. Logistic regression will be used for attainment of post-stroke hypertension treatment goal of <130/80 controlling for any differences in baseline variables.

For Aim 2, we will assess how a subset of questions in PERSNET predict the set of network members who were engaged in the intervention. We will calculate positive predictive value of the subset questions versus full network survey questions.

10. Monitoring and Quality Assurance

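### Physical function is scored only at week 12 and its model fixes no baseline covariate, so precision that stroke severity and age could supply is mostly left unused

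*Combined protocol and SAP*

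**What the plan says.** Physical function is one of two secondary outcomes: "Secondary outcomes will be attainment of a post-stroke hypertension treatment goal and patient-reported physical function" (section 6.4). In the control arm the nurse assesses "the patient-reported physical function (based on the NIH PROMIS physical function sub-scale" at the week-12 session. In the social network arm the patient is to "complete the PROMIS physical function scale, and remap their network with the PERSNET instrument" at that same session. The Data Collection Schedule agrees: PROMIS stands in the end line row for both arms and in no earlier row.

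At baseline, section 6.1 lists "baseline questionnaires consisting of the validated PERSNET social networks questionnaire, stroke information, and the CES-D depression screen", and says that further covariates will be taken from the health record. The schedule adds age, sex, stroke severity and the comorbidity index. No physical function measure is listed.

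For the analysis, section 9.3 states: "Evaluation of the primary outcome and physical function secondary outcome will be completed using linear". I read this as linear regression. The sentence goes on to control for baseline variables that differ between arms. It names no covariate and does not say how a difference is judged.

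On the design side, section 5.1 states: "Patients will be stratified according to network size (<5 vs 5 or more) and location of hospitalization (MGH or BWH". Neither factor is stroke severity, age or function, and section 9.3 does not name either as a model term.

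**The concern.** Adjusting for a baseline variable helps because the variable predicts the outcome, not because it differs between arms. A rule that admits covariates only when they differ discards most of the available gain and makes the final model depend on the data. The effect is most direct for physical function: it is the only outcome compared between the randomised arms whose own measure is not scheduled at baseline, so other prognostic variables must do the work.

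At stake is the width of the confidence interval for this outcome, and how far one trial's estimate may be shifted by arms that differ by chance in initial disability. A pilot's estimates are likely to inform a later trial, so a tighter and reproducible estimate is worth having.

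**Working it through.** **1. The plan's own figure.** Section 9.2 assumes a systolic pressure SD of 13, a difference of 10 mm Hg, alpha 0.05 (two-sided reproduces the figure) and 80% power. Then n per arm = 2 × (1.96 + 0.842)² × 13² / 10² = 2 × 7.85 × 1.69 = 26.5, so 27 per arm and 54 in total, as stated. Enrolling 60 leaves room for 10% loss (54/60 = 0.90). This concerns blood pressure only; no SD, effect or power is given for PROMIS. I take 27 per arm as the evaluable number and work in SD units of the week-12 score.

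**2. Unadjusted standard error.** √(2/27) = 0.272 SD.

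**3. Exposure to chance imbalance.** The difference between arms in any standardised baseline covariate has the same standard error, 0.272. The probability that it exceeds 0.25 SD in either direction is 2 × [1 − Φ(0.25/0.272)] = 36%; for 0.5 SD it is 6.6%. An imbalance of 0.25 SD shifts the unadjusted contrast by ρ × 0.25, where ρ is the covariate's correlation with week-12 PROMIS: 0.075, 0.125 or 0.175 SD at ρ = 0.3, 0.5 or 0.7. The documents give no ρ, so these values are an assumed range.

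**4. What the planned rule recovers.** The criterion is not stated, so I assume p<0.05 on the baseline difference. A simulation with one covariate, 27 per arm and 10,000 runs for each ρ gave these empirical standard errors (SD units):

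| ρ | never adjust | adjust only if p<0.05 | always adjust | runs adjusted under the rule |
|---|---|---|---|---|
| 0.3 | 0.271 | 0.268 | 0.260 | 4.6% |
| 0.5 | 0.273 | 0.264 | 0.238 | 5.0% |
| 0.7 | 0.271 | 0.255 | 0.197 | 4.5% |

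At ρ = 0.5 the rule recovers (0.273² − 0.264²) / (0.273² − 0.238²) = 0.0048 / 0.0179 = 0.27, about a quarter of the variance reduction. Type I error under the rule was 4.5%, 4.3% and 3.7%, so it is conservative, not inflated.

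**5. Fixed adjustment for two covariates.** Here ρ is the joint (multiple) correlation of stroke severity and age with week-12 PROMIS. The variance is multiplied by (1 − ρ²) × (N − 3)/(N − p − 3). The second term is the approximate cost of estimating p covariates. With N = 54 and p = 2 it is 51/49 = 1.041.

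| joint ρ | 1 − ρ² | × 1.041 | variance reduction | standard error (SD) |
|---|---|---|---|---|
| 0.3 | 0.91 | 0.947 | 5% | 0.272 × √0.947 = 0.265 |
| 0.5 | 0.75 | 0.781 | 22% | 0.272 × √0.781 = 0.240 |
| 0.7 | 0.51 | 0.531 | 47% | 0.272 × √0.531 = 0.198 |

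**The case against.** The strongest reply is that nothing here is invalid. Allocation is randomised 1:1, the outcome is defined as physical function and not as change in function, and the standard error of an endpoint-only comparison already allows for chance imbalance. This stands. A reader might infer that a single week-12 score cannot separate an intervention effect from a baseline imbalance, or that the comparison is biased. The documents do not support either reading.

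A reader might also infer that an imbalance in function cannot be removed at all. That goes too far. Severity, age and comorbidity are collected, and section 9.3 would adjust for them if they were judged to differ, which would remove part of an imbalance. Nor do the documents exclude some functional covariate: the stroke information is not itemised, and section 6.1 leaves the list from the health record open. What remains is that none of these is guaranteed.

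The size is fairly disputed too. Nothing in the documents shows how strongly severity predicts week-12 function. Patients with an NIHSS up to 21 are eligible, but the exclusions for aphasia, dementia, lack of capacity and inability to text may narrow the range. The gain could sit near the 5% end. A criterion looser than p<0.05 would adjust more often; a threshold of 0.25 SD, for example, would be crossed in 36% of trials for each covariate. Stratifying on network size, which section 3 ties to stroke recovery, may balance prognosis slightly.

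Finally, this is a secondary outcome of a 60-patient pilot with no power claim attached. That limits the importance of the point but does not remove it, because the main remedy uses data already collected.

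**Conclusion.** The point holds as one of efficiency. PROMIS is scheduled only at week 12, and section 9.3 guarantees no prognostic covariate in its model. The comparison stays unbiased in expectation and the primary sample size is unaffected.

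Under a p<0.05 reading, the planned rule recovers about a quarter of what fixed adjustment for the same covariate would give. Fixed adjustment for severity and age would reduce variance by roughly 5% to 47%, with 22% at a joint correlation of 0.5. These figures rest on 27 evaluable patients per arm, assumed correlations and an assumed criterion for a difference.

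A reader might go further and conclude that a baseline PROMIS score is what the trial lacks. The reductions above do not show that: they describe the covariates jointly, and the extra gain from PROMIS beyond severity and age cannot be derived from the documents. It may be small for a score taken in hospital within 14 days of stroke.

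**What to change.** **Main change.** In section 9.3, for the physical function model, replace the adjustment for whichever baseline variables differ with fixed, pre-specified adjustment for baseline stroke severity and age, whether or not they differ by arm. State the form in which each enters, and make the change before outcome data are examined by arm. Both variables are already in the Data Collection Schedule, so the cost is a protocol edit and two model degrees of freedom, which the figures above already allow for.

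**Optional.** If enrolment is still open, which the documents do not say, add the same PROMIS physical function form to the baseline visit in both arms before randomisation, and include it as a covariate. This adds some burden to a bedside visit that already holds several questionnaires. Patients already enrolled would lack the score, so the analysis would need a stated rule for the missing baselines.

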6.5 Data Collection Schedule

Time point	Individual Counseling Arm	Social Network Arm
Baseline (Week 0)	
Written consentPERSNETDemographics and stroke data (Age, Sex, Stroke severity, Charlston comorbidity index)Blood pressure measure under direct observation	
Written consentPERSNETDemographics and stroke data (Age, Sex, Stroke severity, Charlston comorbidity index)Blood pressure measure under direct observationNetwork members contact info
Session 1 (Week 2 (+/- 7 days))	
BP measure under direct observationFeasibility measures: number of participants, time of session, connection problems.	
BP measure under direct observationFeasibility measures: number of participants, time of session, connection problems.
Session 2 (Week 6 (+/- 7 days))	
BP measure under direct observationFeasibility measures: number of participants, time of session, connection problems.	
BP measure under direct observationFeasibility measures: number of participants, time of session, connection problems.
End line (Week 12 (+/- 7 days))	
BP measure under direct observationPERSNETPROMISFeasibility measures: number of participants, time of session, connection problems.	
BP measure under direct observationPERSNETPROMISCaregiver burden (primary caregiver)Intervention process evaluation (qualitative semi-structured interview)Feasibility measures: number of participants, time of session, connection problems.
Upon completion of study (or after withdrawal)	
Implementation survey or qualitative interview	
Implementation survey or qualitative interview

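### At week 12 a research-only group interview precedes the outcome blood pressure reading in the social network arm only, so conditions before the reading can differ by arm

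*Combined protocol and SAP*

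**What the plan says.** Section 6.4 sets an explicit order for the social network arm at week 12. It opens with the interview: "In this session, the study nurse will first conduct a semi-structured interview with the patient and network members". Next: "All network members will then be asked to leave the Zoom meeting, except for the primary caregiver (if applicable"). The reading follows: "The patient will collect a final blood pressure measurement under direct supervision of the study nurse", and after it the PROMIS and PERSNET instruments.

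For the individual counselling arm the same section says: "In this session, the patient will check their blood pressure under direct video observation by the nurse". This is the first activity listed, but no word fixes its place relative to counselling or anything else.

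The interview is a research step confined to one arm. The Outcomes text in 6.4 describes it so: "The intervention process evaluation conducted using semi-structured qualitative interviewing during the final session (Social Networks arm"). The schedule in 6.5 (Data Collection Schedule) lists "Intervention process evaluation (qualitative semi-structured interview") in the End line row under the social network column only. The implementation survey or interview open to both arms takes place after completion or withdrawal, so it does not balance the week-12 visit.

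Section 9.3 says the outcomes are assessed in both arms in a ten-minute Zoom exit interview observed on video by the nurse. It gives no position for the reading, no preparation and no rule on who is present.

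**The concern.** The primary outcome is the absolute reduction in systolic pressure at 3 months, and attainment of <130/80 is a secondary outcome. Both use this one supervised reading. If what happens just before the reading affects it, and that differs by arm, the difference enters the treatment contrast. It would reflect a data-collection procedure and not the counselling or teamwork under test. Two features of the session differ as written: a group interview before the reading, and the possible presence of the primary caregiver during it.

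Section 9.3 adjusts for differences in baseline variables. An offset created at week 12 is not a baseline difference, so that adjustment leaves it in place. This makes the order worth settling at the design stage.

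**Working it through.** **1. The plan's own figure.** Section 9.2 gives SD 13 mm Hg, a difference of 10 mm Hg, alpha 0.05 and 80% power, with 27 per arm (54 in total). Sidedness is not stated. The two-sided normal formula gives

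n per arm = 2 × (1.960 + 0.842)² × 13² / 10² = 26.5, rounded up to 27.

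The stated figure is reproduced. With a t-test, power at 27 per arm is 79%, and that is the reference value below.

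**2. Why baseline adjustment does not help.** Let the week-12 conditions add δ mm Hg to the mean intervention-arm reading. Randomised arms have the same expected baseline values, so a regression on arm and baseline variables estimates (true effect + δ). Adjustment reduces the residual variance but does not change δ.

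**3. Illustration of size.** The documents give no δ, so the values here are assumed.

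- SE = 13 × √(2/27) = 3.54 mm Hg, with 52 degrees of freedom and critical value 2.007.
- Type I error when there is no true effect is P(|T| > 2.007), where T is noncentral t with noncentrality δ/3.54.
- If δ raises intervention-arm readings, it masks benefit. Power for a true 10 mm Hg effect then uses noncentrality (10 − δ)/3.54.

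| Assumed δ (mm Hg) | δ/SE | Type I error | In the shift's direction | In the other direction | Power for 10 mm Hg if δ masks benefit |
|---|---|---|---|---|---|
| 0 | 0 | 5.0% | 2.5% | 2.5% | 79% |
| 1 | 0.28 | 5.9% | 4.6% | 1.3% | 70% |
| 2 | 0.57 | 8.6% | 8.0% | 0.6% | 60% |
| 3 | 0.85 | 13.2% | 13.0% | 0.3% | 49% |
| 5 | 1.41 | 28.4% | 28.3% | 0.04% | 28% |

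From 2 mm Hg upwards, almost all of the type I error lies in the direction of the shift. A shift that lowers intervention-arm readings would produce false claims of benefit. A shift that raises them would make such claims rarer and would cost power. At 0.5 mm Hg, type I error is 5.2%.

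**4. With baseline adjustment.** Assume a baseline-to-week-12 correlation r. The residual SD is 13 × √(1 − r²), which is 12.40, 11.26 and 9.28 for r = 0.3, 0.5 and 0.7, with 51 degrees of freedom. A 3 mm Hg shift then gives type I error of 14.1%, 16.1% and 21.4%. The shift stays whole while the standard error shrinks.

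**5. Partial participation.** The text on consent to the recorded interview says: "Patients will not be forced to participate and may withdraw their consent to participate at any time". If 70% or 50% of the arm took part (assumed), a 3 mm Hg shift would average 3 × 0.7 = 2.1 or 3 × 0.5 = 1.5 mm Hg. Unadjusted type I error would be 9.0% or 7.0%.

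**The case against.** The strongest reply is that no effect is shown. Nothing in the documents says that an interview changes a later reading, and every shift above is assumed. At 0.5 to 1 mm Hg the test is almost nominal. This stands, and it limits the weight of the point.

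A second reply is that controls may also talk first. Section 6.4 calls week 12 the third counselling session for both arms, and at week 2 (section 6.3a) the control reading is listed after counselling. The real contrast may be one conversation against another. This also stands. A reader might infer that one arm talks while the other sits quietly, but the documents do not support that, because the control reading has no stated position.

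Third, section 9.3 describes a common exit interview. In 6.4, once network members leave, the remaining steps (blood pressure, PROMIS, PERSNET) match the control list. That can be read as a shared assessment block after the group part. It narrows the difference but does not remove the preceding interview or the caregiver exception.

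Fourth, one sentence in 6.4 is incomplete: "The semi-structured interviews after the will be audio recorded". The gap may come from text extraction, and the missing words might bear on the order. It is not counted here as a defect. The order rests on the intact sentences.

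A reader might also take 28.4% as a false-efficacy rate. That would need a 5 mm Hg shift that lowers intervention-arm readings, and the documents give neither that size nor that direction.

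**Conclusion.** The point holds as a difference in measurement conditions that the plan itself sets out. Following 6.4 as written places a research-only interview, and possibly a caregiver's presence, ahead of or around the outcome reading in one arm only. No other section equalises this. It is more than missing detail, because the order in the social network arm is stated.

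It does not establish that the trial's result will be biased. Size and direction are unknown, and the offset may be small. The figures rest on assumed shifts, the plan's SD of 13 mm Hg, 27 per arm and a two-sided 5% test. On that basis the consequence runs from negligible at or below 1 mm Hg to material at 3 mm Hg or more, as inflated type I error or lost power depending on direction. Severity is minor to should-fix. The stated sample size of 54, with 60 enrolled, is unaffected.

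**What to change.** In 6.4, state one procedure for both arms. Suggested text: *At the start of the week-12 session, after the same preparation in both arms, with only the patient and study staff on the call and before any interview, counselling, PROMIS or PERSNET, the patient takes the supervised blood pressure reading. In the social network arm, network members then join and the group interview follows.* The study team should define the preparation once for both arms. Align the 6.5 Data Collection Schedule and the exit interview in 9.3 with this order.

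The cost is a short amendment and a re-ordered visit, with no added visit, staff or measurement. There are three downsides:

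- Network members, including the primary caregiver, join a few minutes later, so joining has to be staggered.
- Patients take their own reading, so they will know it before an interview about effectiveness. Postponing discussion of the result cannot hide it.
- The order will differ from week 2, where the reading is listed after counselling.

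If the team prefers to keep the reading late in the session, stating the same position, preparation and people present for both arms, with the interview after the reading, would meet the same need.
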